8.1.7 Investigator asthma knowledge questionnaire

Asthma knowledge questionnaire for investigator is designed base on CPH survey and asthma guideline. More details in Appendix D.

8.1.8 Inhaler skill score assessment

Regarding the technical standards of inhalation, there are relevant regulations in national guidelines, and the overall process is consistent ([Chinese expert consensus on standard application of inhalation device in stable chronic airway disease patients, 2019](#)). Regarding the technical standards of inhalation, there are relevant regulations in national guidelines, and

the overall process is consistent (Chinese expert consensus on standard application of inhalation device in stable chronic airway disease patients, 2019). The study is designed for 7 steps, with 1 point for each step, and the full score is 7 points. The technical evaluation of inhaler is based on devices which commonly used by researchers participating in the study. Inhaler skill shall be assessed by the group from leading site before and after education, and the subjects shall be instructed only after investigators pass this assessment. Random inspections will be conducted during the follow-up period. V1 allows the subjects to demonstrate the inhalation process such as the dosing or the using method with the prepared device, and the researcher controls the operating standard as the baseline. It is recommended that each centre recommend 1-2 physicians or nurses, who are trained and qualified to be responsible for this work, and adopt uniform standards. (Appendix E)

8.1.9 Questionnaire for Asthma Patients during COVID-19

The design of the questionnaire for Asthma patients during COVID-19 refers to the Chinese Cough Alliance “COVID-19 Infection Cough Characteristics and Prognosis Survey Version 1.0” (released in January 2023). If the patient got COVID-19 infection, then answer the questionnaire, the uninfected patients are not necessary to response. Every subject if has a new infected with COVID-19 should answer one time .

8.2 Safety Assessments

Not applicable.

8.3 Collection and Reporting of Adverse Events/Adverse Drug Reactions

8.3.1 Collection of Adverse Events

The Principal Investigator is responsible for ensuring that all staff involved in the study are familiar with the content of this section. The definitions of an AE or SAE can be found in Appendix B.

Adverse Events related to AZ product will be collected from the time of starting the study throughout follow-up period specified in the protocol. Regardless the relationship with AZ products, all SAEs will be actively collected. Investigators and/or site staff should report the SAEs to study representatives within 24 hours from awareness, and study representatives need to report the SAEs to AstraZeneca Data Entry Site (AZ DES) within 5 days. For fatal or life-threatening SAEs, the reporting to AZ DES should be within 1 day.

Any AEs that are unresolved at the patient's last AE assessment or other assessment/visit as appropriate in the study are followed up by the Investigator for as long as medically indicated, but without further recorded in the CRF. AstraZeneca retains the right to request additional

information for any patient with ongoing AEs/SAEs at the end of the study, if judged necessary.

8.3.2 Reporting of Serious Adverse Event (SAE)

All SAEs have to be reported, whether or not considered causally related to the AstraZeneca product, or to the study procedure(s). All SAEs will be recorded in the CRF.

If any SAE occurs in the course of the study, then Investigators or other site personnel will inform the appropriate AstraZeneca representatives within one day i.e., immediately but no later than 24 hours of when he or she becomes aware of it.

For fatal or life-threatening adverse events where important or relevant information is missing, active follow-up is undertaken immediately. Investigators or other site personnel inform AstraZeneca representatives of any follow-up information on a previously reported SAE within one calendar day i.e., immediately but no later than 24 hours of when he or she becomes aware of it.

8.3.3 Reporting of non-serious Adverse Drug Reaction (ADR)

Any non-serious ADR related to AZ product occurs in the course of the study must be reported per the China regulation.

If any non-serious ADR related to AstraZeneca products occurs in the course of the study, then investigators or other site personnel should inform the AstraZeneca representatives within 5 calendar days when he or she becomes aware of it.

8.3.4 Reporting of Special Situations

Special situations are situations of relevance for monitoring the safety of AZ products and which may or may not be associated with an AE. The investigator must inform the Sponsor Study Representative immediately but no later than 24 hours after becoming aware of any special situation reports.

Individual case safety reports (ICSRs) with special situations will be entered into the AZ Global Safety Database, regardless of whether they are associated with an AE or not. The Sponsor Study Representative will ensure special situation reports without associated SAEs are reported to AZ DES within 30 days of awareness.

8.3.4.1 Overdose

Investigators are advised that any patient, who receives a higher dose than indication use should be monitored closely, managed with appropriate supportive care, and followed up expectantly.

- An overdose with associated AEs is recorded as the AE diagnosis/symptoms on the relevant AE modules in the CRF and on the Overdose CRF module.
- An overdose without associated symptoms is only reported on the Overdose CRF module.

If an overdose on an AstraZeneca drug occurs in the course of the study, then the Investigator or other site personnel inform appropriate AstraZeneca representatives immediately, or no later than 24 hours of when he or she becomes aware of it.

The designated AstraZeneca representative works with the Investigator to ensure that all relevant information is provided to the AstraZeneca Patient Safety data entry site.

8.3.4.2 Pregnancy

All pregnancies and outcomes of pregnancy should be reported to AstraZeneca.

8.3.4.2.1 Maternal exposure

If a patient becomes pregnant during the course of the study, the outcomes of any conception occurring from the date of the first dose of study medication until 1 month after the last dose of AstraZeneca medication must be followed up and documented.

Pregnancy itself is not regarded as an adverse event unless there is a suspicion that the investigational product under study may have interfered with the efficacy of a contraceptive medication. Congenital abnormalities/birth defects and spontaneous miscarriages should be reported and handled as SAEs. Elective abortions without complications should not be handled as AEs. The outcome of all pregnancies (spontaneous miscarriage, elective termination, ectopic pregnancy, normal birth or congenital abnormality) should be followed up and documented even if the patient was discontinued from the study.

If any pregnancy occurs during the course of the study, then the Investigator or other site personnel informs the appropriate AstraZeneca representatives immediately, or no later than 24 hours of when he or she becomes aware of it.

The designated AstraZeneca representative works with the Investigator to ensure that all relevant information is provided to the AstraZeneca Patient Safety data entry site.

The same timelines apply when outcome information is available.

8.3.4.2.2 Paternal exposure

Pregnancy of the patient's partners is not considered to be an AE. However, the outcome of all pregnancies (spontaneous miscarriage, elective termination, ectopic pregnancy, normal birth or congenital abnormality) should, if possible, be followed up and documented. If allowed by

local regulations, information about a pregnancy from the partner of a male patient can be captured. If so, the male patient's partner consent must be obtained to collect information related to the pregnancy and outcome; the male patient should not be asked to provide this information. A consent form specific to this situation must be used. The outcome of any conception occurring from the date of the first dose until 6 months after dosing must be followed up and documented.

8.3.4.3 Medication errors

For the purposes of this clinical study a medication error is an unintended failure or mistake in the treatment process for AstraZeneca products that either causes harm to the patient or has the potential to cause harm to the patient. A medication error is not lack of efficacy of the drug, but rather a human or process related failure while the drug is in control of the study site staff or patient.

Medication error includes situations where an error:

- Occurred
- was identified and intercepted before the subject received the drug
- did not occur, but circumstances were recognized that could have led to an Error

Examples of events to be reported in clinical studies as medication errors:

- Drug name confusion
- Dispensing error, e.g., medication prepared incorrectly, even if it was not actually given to the patient
- Drug not administered as indicated, for example, wrong route or wrong site of administration
- Drug not taken as indicated, e.g., tablet dissolved in water when it should be taken as a solid tablet
- Drug not stored as instructed, e.g., kept in the fridge when it should be at room temperature
- Wrong drug administered to patient

Medication errors are not regarded as AEs but AEs may occur as a consequence of the medication error.

If a medication error occurs in the course of the study, then the Investigator or other site personnel informs the appropriate AstraZeneca representatives immediately, and no later than 24 hours of when he or she becomes aware of it.

8.3.4.4 Other Special Situations

Besides situation above, other special situations related to AZ products should be collected, the Investigator or other site personnel informs the appropriate AstraZeneca representatives immediately, and no later than 24 hours of when he or she becomes aware of it:

- Exposure to product whilst breastfeeding
- Off label use/product use issue
- Drug Abuse
- Drug Misuse
- Occupational exposure
- Product Quality Complaints/issues (PQCs) incl. Counterfeit/Falsified product
- Lack of efficacy and disease progression
- Medical Device/Device Constituent Part malfunction or deficiency

8.4 Human Biological Samples

In the study, there is no proactively intervention to collect biological samples for any assessment. Clinical laboratory data will be collected if available in medical record as specified in the SoA.

8.5 Human Biological Sample Biomarkers

Not applicable.

8.6 Optional Genomics Initiative Sample

Not applicable.

8.7 Healthcare Resource Utilization (HCRU)

Not applicable.

9 STATISTICAL CONSIDERATIONS

9.1 Statistical Hypotheses

The change in GINA guideline-recommended treatment after guideline education and implementation, will be compared between the proportion of patients on with an ICS-based maintenance and/or reliever treatment at Week 48 and the proportion at baseline. For each treatment arm, the proportions along with the 95% confidence intervals the rates and the difference Δ will be computed. The hypothesis test is formed as follows:

The null hypothesis to be tested is:

H_0 : Proportion of patients with ICS-based maintenance and/or reliever treatment at baseline =
Proportion of patients with ICS-based maintenance and/or reliever treatment at Week 48

Against the alternative hypothesis:

H_a : Proportion of patients with ICS-based maintenance and/or reliever treatment at baseline \neq
Proportion of patients with ICS-based maintenance and/or reliever treatment at Week 48

9.2 Sample Size Determination

Approximately 1500 participants will provide 80% power at a significant level of 0.05 to detect a change from baseline in the proportion of patients with an ICS-based maintenance and/or reliever treatment at week 48 of 5% (Zhao et al 2014). The baseline proportion is assumed to be 40% and a within-participants correlation is assumed to be 0.25. The proportion of missing postbaseline assessment at week 48 is assumed to be 30%.

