The change in GINA guideline-recommended treatment after guideline education and implementation, will be compared between the proportion of patients on with an ICS-based maintenance and/or reliever treatment at Week 48 and the proportion at baseline.

Sample Size Estimations:

Approximately 1500 participants will provide 80% power at a significant level of 0.05 to detect a change from baseline in the proportion of patient on the treatment in accordance with GINA recommendations at Week 48 of 5%. The baseline proportion is assumed to be 40% and a within-participants correlation is assumed to be 0.25. The proportion of missing postbaseline assessment at week 48 is assumed to be 30%.

Statistical Analysis:

General Rules

Unless otherwise stated, all the descriptive summary in this study will be based on the following general methods.

All categorical data will be presented in contingency tables, using absolute and relative frequencies. Percentages will be rounded to the first decimal place and, therefore, may not always add up to 100%. When applicable, 95% confidence intervals (CIs) will be presented with estimates of proportions.

[figure not shown]
All continuous data will be summarized via relevant descriptive statistics, such as number of observations with available measurements, mean, standard deviation, median, first and third quartiles (Q1 and Q3) when applicable, minimum and maximum.

Primary Analysis

The primary analysis will use mixed effect logistic regression model, taking the measurement timepoint (baseline/post- baseline) as the fixed effect, hospital, pulmonologist and patient as the random effects. In case of lack of convergency, hospital and prescriber factors will be removed from the model. Within the framework of this model, the 95% confidence interval of the primary endpoint will be estimated and presented. The analysis will be based on FAS population.

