The intervention will be targeting pulmonologists at site hospitals. To reflect the real world practice, all pulmonologists attending outpatient clinics will be expected to recruit patients. However, depending on the scale of the selected hospitals and actual study operation, the number of participating pulmonologists will vary, as well as the number of pulmonologists who recruit patients, and the number of patients recruited per pulmonologists. These variations may introduce biases into this study. During the study conduct, patient recruitment will be closely monitored for unusual pattern. In addition, the statistical analyses will take into account the within-hospital and within-pulmonologist correlation, by including the hospital and pulmonologist effect into the model as random effect.

Retrospective data based on electronic medical records (EMR) offers a potential source of data collection. However, the original purpose of collecting EMR is for clinical care

management rather than research purpose, so there are inherent limitations in using EMR data to conduct clinical research, e.g., information incompleteness and data inaccuracy. Some data required by the protocol, e.g., ACQ-5 and AQLQ(S)+12, are not routinely collected in clinical practice. As this is a pragmatic study, patients can potentially go to any hospitals or pulmonologists for care during the study and EMR data from site hospitals will not be able to capture all the information. Given these inherent limitations of EMR data, we choose to prospectively collect data from patients in this study.

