9.4.2 Effectiveness

9.4.2.1 Primary Endpoint(s)

Change from baseline in the proportion of patients with an ICS-based maintenance and/or reliever treatment at week 48

Prescription will be used to define this endpoint. The primary analysis will use mixed effect logistic regression model, taking the measurement timepoint (baseline/post-baseline) as the fixed effect, hospital, pulmonologist and patient as the random effects. In case of lack of convergency, hospital and pulmonologist factors will be removed from the model. Within the framework of this model, the 95% confidence interval and p value of the primary endpoint will be estimated and presented. The analysis will be performed in FAS.

Another sensitivity analysis will be conducted with generalized estimating equations (GEE) model using the same covariates as the primary analysis.

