4.2.1.2 Primary Analysis of Primary Endpoint

Proportion of patients with an ICS-based maintenance and/or reliever treatment will be described using the frequency with ICS and corresponding percentage at baseline and week 48.

The primary analysis will use mixed effect logistic regression model, taking the measurement timepoint (baseline/post-baseline) as the fixed effect, hospital, pulmonologist and patient as the random effects. Logit link function will be used, and the model parameters will be estimated by maximum likelihood approach. The compound-symmetry variance-covariance structure will be used. In case of lack of convergency, hospital and prescriber factors will be removed from the model.

Within the framework of this model, first predict for all patients the probability of ICS usage at baseline/ post-baseline and then take the average over baseline/ post-baseline patients to get an estimate of proportion, and finally take the difference between the two proportions as the risk difference estimate, the 95% confidence interval of risk difference in proportion by bootstrapping method will be estimated and presented. Besides, Odds Ratio and P value from the model will also be estimated and presented. The analysis will be performed in FAS. Reference SAS code is shown in section 7.

If medication is taken at least once within 3 months before Visit 0 (week -12), the patients will be regarded as taking this medication at baseline. For Visit 2 (week 12), if medication is taken at least once on or after Visit 1 and on or before Visit 2 (within 3 months before this visit), the subjects will be regarded as taking medications at this visit. For Visit 3 -Visit 5 (week 24, 36 and 48), if medication is taken at least once after last visit and on or before this visit (within 3 months before this visit), the subjects will be regarded as taking medication at this visit.

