7 APPENDIX

7.1 SAS sample code for proc GLIMMIX

```
proc GLIMMIX data=ics;  
  
class visit (ref='0') hosp doct;  
  
model mpd = visit / dist=binary link=logit oddsratio solution;  
  
contrast 'week 48 vs baseline' time [1,4][-1,5] ;  
  
random subjid hosp doct;  
  
run;
```

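### The 80% power figure leaves no room for the change to differ between hospitals, and no written step of the primary or sensitivity analysis clearly allows for it

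*Protocol*

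**What the plan says.** **Power.** Protocol 9.2 states: "Approximately 1500 participants will provide 80% power at a significant level of 0.05 to detect a change from baseline in the proportion" of patients on ICS-containing treatment at week 48, the change being 5%. The other inputs are a 40% baseline, 30% missing at week 48, and, as the Synopsis puts it, "a within-participants correlation is assumed to be 0.25". SAP 1.3 repeats these. No hospital or pulmonologist quantity is listed.

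**Promise.** Protocol 6.7 says the analyses will "take into account the within-hospital and within-pulmonologist correlation, by including the hospital and pulmonologist effect into the model as random effect".

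**Primary model.** Protocol 9.4.2.1 and SAP 4.2.1.2 take timepoint as the fixed effect, with "hospital, pulmonologist and patient as the random effects". SAP 4.2.1.2 adds: "The compound-symmetry variance-covariance structure will be used", without naming the effect it applies to. The sample code in SAP 7.1 has "random subjid hosp doct" and no hospital-by-visit term.

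**Interval.** SAP 4.2.1.2 says "the 95% confidence interval of risk difference in proportion by bootstrapping method will be estimated and presented". It does not say whether patients or hospitals are resampled.

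**Fallback.** "In case of lack of convergency, hospital and prescriber factors will be removed from the model" (SAP 4.2.1.2; Protocol 9.4.2.1 has the same rule).

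**Sensitivity analysis.** The GEE in SAP 4.2.1.3 and 7.2 uses the patient as the cluster.

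**The concern.** The intervention acts on hospitals, and the design gives them different exposure. Each department's PI arranges the reinforcement sessions, their frequency can fall when that department meets its KPI threshold (Protocol 6.1.2.1), and the main topics are taught by a regional expert (6.1.2.5). A change that is identical everywhere is therefore a strong assumption, and the plan neither states nor defends it.

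A random hospital intercept describes differences in level. In a before-after comparison within patients these largely cancel, so the intercept does little for the standard error of the change. What matters for that standard error is how far the change itself varies between hospitals. If this is left out, the test of the one primary hypothesis can reject too often. The stated 80% would then also be more than a test that respects the hospital clustering can deliver.

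**Working it through.** **Inputs from the documents.** Baseline 0.40, week 48 0.45, correlation 0.25, 30% missing, N = 1500, two-sided alpha 0.05 (the alternative in Protocol 9.1 is two-sided), about 30 hospitals (Protocol 4.1).

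**Assumed.** The SD of the true change between hospitals, called tau, because the documents give none; equal hospital size; all 1500 baselines analysed.

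**1. Reproducing the stated figure, no hospital term.**

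V = p1q1 + p2q2/0.7 − 2·rho·√(p1q1·p2q2) = 0.24 + 0.2475/0.7 − 2(0.0609) = 0.4717.

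n = 7.849 × 0.4717 / 0.05² = 1481, against about 1500 stated.

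At N = 1500, SE0 = √(0.4717/1500) = 0.01773 and power is Φ(0.05/0.01773 − 1.96) = 80.5%. The stated figure is therefore sound arithmetic for tau = 0.

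**2. Adding variation in the change.** SE = √(SE0² + tau²/30).

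- Type I error when tau is ignored: 2[1 − Φ(1.96·SE0/SE)].
- Power of a hospital-aware test: Φ(0.05/SE − 1.96), or noncentral t on 29 df with noncentrality 0.05/SE.

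| tau (points) | SE | Type I error, tau ignored | Hospital-aware power, normal | Hospital-aware power, t29 |
|---|---|---|---|---|
| 0 | 0.0177 | 5.0% | 80.5% | 77.8% |
| 2 | 0.0181 | 5.5% | 78.9% | 76.1% |
| 5 | 0.0199 | 8.1% | 70.8% | 67.8% |
| 10 | 0.0255 | 17.2% | 50.2% | 47.6% |

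**3. Do hospital intercepts help?** Simulation used 30 hospitals of 50 patients, 30% missing at random at week 48, within-patient correlation 0.25, and assumed logit SDs of 0.3 for hospital and 0.2 for pulmonologist. Results are at tau 0/2/5/10.

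| Test, no true mean change | Type I error |
|---|---|
| Mixed logistic, hospital and patient intercepts (pulmonologist not fitted) | 4.8/4.7/9.0/18.2% |
| Patient-clustered standard error | 5.5/5.7/8.6/17.7% |
| Hospital-clustered standard error, t29 | 5.0/5.3/5.4/4.4% |

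The intercept-only model behaves like the patient-clustered one.

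**4. Bootstrap interval.** This was run on the difference in observed proportions, as a stand-in for the model-averaged difference in SAP 4.2.1.2. Coverage of 95% percentile limits at the same tau values:

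- Resampling patients: 94.6/94.8/90.3/81.3%.
- Resampling hospitals: 93.3/94.1/92.7/93.0%.

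Undercoverage that grows with tau appears only when patients are resampled. Monte Carlo error is about 0.5 points at a rate of 5%.

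**The case against.** **The target of inference is open.** The null hypothesis in Protocol 9.1 names no wider set of hospitals, and Protocol 5.1 selects sites by volume, drug availability and willingness. If inference is to these hospitals only, differences between them are not sampling error and the problem disappears. This stands as a condition. The aim of representing real-world practice (4.1), the wish to inform a future training model (2.2) and the random hospital effect point to the wider reading, but they do not settle it.

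**The size is assumed.** Nothing in the documents fixes tau. At 2 points the effect is trivial. The type I figures also take a zero mean change with hospitals moving both ways. This stands.

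**Stronger readings the documents do not support.**

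- A reader might infer that hospital is ignored. It is in the model; what is missing is variation of the change.
- A reader might infer that the planned confidence interval is too narrow. The resampling unit is unstated, and resampling hospitals fits the text equally well.
- A reader might take the code as proof of a deliberate omission. As printed, SAP 7.1 leaves subjid off its CLASS statement and writes its CONTRAST on a variable that is not in the model, so it is weak evidence of intent. If the compound-symmetry sentence refers to visits within hospital, the model would already let the change vary.

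**The power base is itself approximate.** The full analysis set requires a post-intervention assessment, so fewer than 1500 baselines may enter. With only 1050 completers, V = 0.24 + 0.2475 − 0.1219 = 0.3656, SE = 0.01866 and power at tau = 0 is 76.4%.

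**A larger effect would still be found.** For a 10-point change at tau = 10, with the same SE, hospital-aware power is 97.6% (96.7% with t29). The power loss matters for changes near 5 points.

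**Conclusion.** The gap is real but conditional. The 80% is correct arithmetic under an unstated assumption: the same change in every hospital. That this is the assumption is an inference, drawn from the absence of any hospital input and the close fit of the formula without one. As the text reads, neither the model p-value nor the GEE standard error carries hospital variation in the change, so Protocol 6.7's promise is only partly met. The non-convergence rule would remove even the hospital intercepts.

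If the hospitals represent a wider set, both tests are anti-conservative to a degree set by tau: slight at 2 points, 8.1% type I error at 5, 17.2% at 10. The bootstrap interval is affected only if patients are resampled. The documents do not show that tau is large, so they do not support calling the trial underpowered or its result unreliable. The change is worth making because it is cheap and protects the single primary test.

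**What to change.** With N unchanged:

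1. Cluster the sensitivity GEE on hospital, with a small-sample correction for about 30 clusters, such as t on 29 df.
2. State that the bootstrap for the primary risk difference resamples whole hospitals.
3. If the mixed model does not converge, move to the hospital-clustered analysis instead of a model with no hospital term. Note that its odds ratio is population-averaged and that it then coincides with the sensitivity analysis.
4. State that the 80% assumes the same change in every hospital, and say to which hospitals inference applies. A short table of hospital-aware power over a range of SDs would serve.

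A hospital-by-timepoint random effect in the primary model is optional, as are refinements to the percentile limits. Without that effect the model's own p-value stays unprotected and should be read beside the hospital-level results. The SAP should also say which effect the compound-symmetry structure applies to.

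**Cost.** SAP wording, sample code and one power sentence; hospital is already a variable in both code samples. At tau = 0 the half-width goes from 1.96 × 1.773 = 3.5 points to 2.045 × 1.773 = 3.6 points, and the stated power from 80.5% to 77.8%. With t29 the half-width would be 4.1 points at tau = 5 and 5.2 at tau = 10. If the optional term is added, non-convergence becomes somewhat more likely.
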